## DEFINITIONS, ACRONYMS, AND ABBREVIATIONS

CCR	Center for Clinical Research
FMR	Functional mitral regurgitation
UMA	Undersizing mitral annuloplasty
IPMS	Inter papillary muscle separation
PMA	Papillary muscle approximation
LV	Left ventricle
MV	Mitral valve
LVEDI	LV End diastolic volume
LVESI	LV End systolic volume index
EF	Ejection fraction
MRF	Mitral regurgitation fraction

## 1.0 PROTOCOL SUMMARY

Title	Improving mitral repair for functional mitral regurgitation (IMPROVE-FMR)
Precis	
Functional mitral regurgitation (FMR) can have an adverse impact on the cardiomyopathic left ventricle, by imposing a chronic low-pressure volume overload. Unrepaired FMR increases the risk of congestive heart failure and death. Undersizing mitral annuloplasty (UMA) is the current gold standard for repair of FMR, but its outcomes are poor with 32.6% of patients presenting with clinically significant recurrent FMR at 1 year after the repair, which increases to 58.8% of the patients at 2 years after annuloplasty. Currently, we do not understand why some patients have failure of annuloplasty, while others do not. Lack of mechanistic insights has inhibited an evidence driven approach in optimizing the repairs adequately – resulting in plethora of new sub-valvular techniques, but very few with appropriate scientific justification to be tested in randomized trials.
 
Our team recently performed a retrospective cardiac MRI study in FMR patients and identified that inter-papillary muscle separation (IPMS) is a strong determinant of FMR severity prior to undergoing any repair. Using image-derived computational biomechanical modeling, we reported that when IPMS is elevated, marginal chordal forces restrict parallelization of the leaflet edges and cause higher FMR. We built upon this observation, and performed an ex vivo bench study to demonstrate that IPMS is a strong determinant of repair success as well. In this study, we demonstrated that the MR volume after repair is directly correlated to the pre-operative IPMS. We recently advanced this study further into a chronic swine model, and demonstrated that swine undergoing papillary muscle approximation (PMA) alone or concomitantly with undersizing mitral annuloplasty (UMA), have better valvular function at 3 months after surgery, compared to animals that receive UMA alone. Their valvular kinematics were superior, and so was their ventricular function.
 
In this observational, prospective, non-randomized study in humans with FMR, we seek to investigate the following:
 

• Question 1: Does pre-operative IPMS correlate with the severity of FMR after UMA at 30 days, 6 months and 12 months. We will study this primary objective by conducting pre-operative MRI and echo in patients receiving UMA, and follow them to one year. Secondly, we will use these images from each patient as input to a computational biomechanical model, which will help demonstrate the chordal forces and stresses before repair, after repair and at the follow-up time points. We will recruit a total of 125 patients to this phase of the study.


	
 
• Question 2: Does reducing IPMS with a papillary muscle approximation stitch reduce the FMR severity after UMA, by improving valve geometry and biomechanics. We will conduct a pilot study of 15 patients with this approach and investigate their outcomes at 1 year after the surgery.
 

Hypothesis	Elevated IPMS is a risk factor for failure of UMA and recurrence of FMR at 12 months the repair. Reducing IPMS with a papillary muscle approximation stitch can reduce FMR recurrence after UMA.
Objectives	
 
(1) Determine if pre-surgery diastolic IPMS, systolic IPMS and (diastolic-systolic) IPMS correlates with the severity of FMR at immediate post-op, 30 days, 6 months, and 12 months post-UMA.
 
(2) Does IPMS reduction with PMA performed concomitantly with UMA, help in reducing the severity of FMR at immediate post-op, 30 days, 6 months, and 12 months after surgery.
 

Primary Endpoints	The primary endpoint of this study is to investigate if pre-operative inter-papillary muscle separation (diastolic, systolic and diastolic-systolic) correlates with FMR severity at 12 months after surgery with UMA and UMA+PMA.
Secondary Endpoints	
Survival
 
 
• All-cause mortality at discharge, 6 months and 1 year
 
 
Functional Status and Hospitalizations
 
 
• MACE (death, stroke, worsening heart failure (+1 NYHA Class), CHF hospitalization, mitral valve re-intervention at 6 months and 1 year
 
• NYHA classification at 6 months and 1 year
 
• 6-minute walk test at 6 months and 1 year
 
• Readmission rates at 6 months and 1 year
 
 
Physiologic
 
Pre-operative:
 
 
• MRI 
 
- MR severity
 
- Interpapillary muscle dynamics
 
- Left ventricular function
 
- Left ventricular geometry
 
- Left ventricular perfusion and motion defects
 
- Left ventricular scar burden
 
 
 
• Echo (transthoracic and transesophageal) 
 
- MR severity (ERO and regurgitant fraction)
 
 
 

	
 
- Mitral valve leaflet kinematics
 
- Mitral gradient and stenosis
 
- Left ventricular function
 
- Left ventricular geometry
 
- Left atrial dimensions
 
- Right ventricular size and function
 
- Regional wall motion
 
 
Intra-operative:
 
 
• Transesophageal Echo 
 
- MR severity (ERO and regurgitant fraction)
 
- Mitral valve leaflet kinematics
 
- LV function
 
 
 
 
Chest closure echo:
 
 
• Transesophageal Echo 
 
- MR severity (ERO and regurgitant fraction)
 
- Mitral valve leaflet kinematics
 
- LV function
 
 
 
 
Discharge:
 
 
• Transthoracic Echo 
 
- MR severity (ERO and regurgitant fraction)
 
- Mitral valve leaflet kinematics
 
- LV function
 
 
 
 
30-days:
 
 
• Transthoracic Echo 
 
- MR severity (ERO and regurgitant fraction)
 
- Mitral valve leaflet kinematics
 
- LV function
 
 
 
 
6 months
 
 
• Transthoracic Echo 
 
- MR severity (ERO and regurgitant fraction)
 
- Mitral valve leaflet kinematics
 
- LV function
 
 
 
 
12 months
 
 
• Cardiac MRI with contrast or Transesophageal echocardiography
 
• Transthoracic Echo 
 
- MR severity (ERO and regurgitant fraction)
 
- Mitral valve leaflet kinematics
 
- LV function
 
 
 

Population	Patients with FMR from either ischemic or non-ischemic cardiomyopathies, referred for surgical or transcatheter mitral valve annuloplasty with or without the need for revascularization. Suitability for mitral annuloplasty is determined by the surgeon, using some or all the criteria described here:

	
 
• Left ventricular end diastolic diameter is less than or equal to 70mm.
 
• Systolic tenting height is less than or equal to 12mm
 

Inclusion criteria	
 
• Mitral regurgitation of moderate or greater severity, as defined by the guidelines of the American society of echocardiography at the time of the study approval (via a transthoracic echo).
 
• Cardiomyopathy of ischemic or non-ischemic origins, with or without the need for coronary revascularization.
 
• Concomitant right sided valve repair or replacement (i.e. patients requiring concomitant tricuspid procedures).
 
• Age <math>\geq 18</math> years
 
• Able to sign informed consent and release of medical information forms, or able to assign a legal representative who can sign on the patient's behalf.
 

Exclusion criteria	
 
• Any evidence of structural (chordal or leaflet) mitral lesions.
 
• Prior mitral valve repair
 
• Contraindication for cardiopulmonary bypass
 
• Clinical signs of cardiogenic shock at the time of recruitment to the study.
 
• ST segment elevation myocardial infarction within 14 days prior to inclusion in this study.
 
• Congenital heart disease (except PFO or ASD)
 
• Chronic renal insufficiency defined by Creatinine <math>\geq 3.0</math> or chronic renal replacement therapy, who are contraindicated for cardiac surgery
 
• Recent history of psychiatric disease that is likely to impair compliance with the study protocol, in the judgement of the investigator
 
• Pregnancy at the time of randomization
 

Study Procedures	
Step 1) Obtain Emory University Institutional Review Board review and protocol approval to begin study.
 
Step 2) Study kick-off meeting, with all investigators and research staff. Study protocol copies to be distributed to each team member. Data coordinators trained to use the study specific redcap database for data entry.
 
Step 3) Recruitment begins.
 
Patients will be recruited to three registries, with the procedures described as follows:
 
Registry # 1: Prospectively Identified Patients that will Receive Surgery after Recruitment and Consented to Participate in the Study
 
Step 4) Subjects are screened based upon medical records, external echo examinations, echo exams performed in the Emory cardiology clinics or cath labs, inclusion and exclusion criteria.
 
Step5) Screened patients are consented and request for release of medical information is signed.
 
Step6) Consented patients undergo battery of baseline tests that are standard of care, including transthoracic echo, transesophageal echo, and cardiac MRI. If some patients have already completed baseline tests as part of their standard of care, and are identified after these are completed, we will consent them at this stage.
 
Step7) Patients undergo surgery, with pre-operative echo and closed chest echo.
 
Step8) Blood draws and echocardiography performed at discharge and 30-days.
 
Step9) Patients return for visits at 6 months and 1 year to undergo repeat of tests.
 
Step10) Patients exit study after the 1st year. If extended follow-up is determined to be necessary, patients will be re-consented at the 1-year visit.
 
Registry # 2: Retrospectively identified patients, who already underwent the standard of care surgery, and were identified after the procedure is completed, and are suitable for recruitment to the study for their post-operative research

-------------------------	--

	
Rationale: The decision to perform mitral valve surgery could be made during the surgery by the surgeon, and these patients would be suitable for this study, but would not be consented prior to their surgery. Thus, in this registry, we will identify such patients for recruitment into this study, as their first research point isn't until 6 months after their surgery.
 
Step 1) Charts will be screened for patients who underwent surgery for the lesion of interest at Emory, who would otherwise be eligible for this study but were not recruited as it was not known if they will need mitral valve surgery.
 
Step 2) Patients who are still within 6 months (<math>\pm</math> 1 month) after the date of their surgery will be contacted after surgery and the study objective will be explained, verbal consent will be obtained and the date to visit Emory will be provided.
 
Step 3) Written consent will be obtained at their 6 month visit, and steps 9 and 10 described in registry # 1 will be performed.
 
Registry # 3: Retrospectively identified patients, who already underwent the standard of care surgery, and were identified after the procedure is completed, and are suitable for recruitment to the study for their post-operative research.
 
Rationale: Historical review of patients between dates 1/1/2004 to present who have undergone mitral valve surgery who were not previously identified in the study. These patients have not been consented prior to their surgery. The purpose is to increase the study sample size in order to gain statistical power for outcome analysis.
 
Step 1) Charts will be screened for patients who underwent surgery between 1/1/2004 to present for the lesion of interest at Emory, who would otherwise be eligible for this study but were not recruited as it was not known if they will need mitral valve surgery or were not recruited as they may have received the surgery prior to study start date.

Sample size	
140 subjects in total at Emory University.
 
Group 1: 125 patients to receive UMA and followed to 12 months, with interim imaging.
 
Group 2: 15 patients to receive UMA with PMA and followed to 12 months, with interim imaging.

	
It is expected that we will recruit ~25 patients per year.
 
Group 3: patients' medical charts will be queried between 2004 – present, number of subject charts are undetermined/unknown.

Risk-benefit determination	
Neither UMA nor PMA are experimental procedures, thus the risk from the procedures itself is considered minimal. Surgeons at our institution have experience with both procedures in humans, albeit with more extensive experience with undersizing mitral annuloplasty and recent preliminary experience with papillary muscle approximation.
 
Proposed pre-operative and post-operative echocardiography and MRI are non-invasive, and thus the risk from these procedures is minimal as well. The data obtained from such imaging may not directly impact the patients care, however if any recurrence of FMR or deterioration in cardiac function is observed from the study imaging, the investigative team will inform the patient to consult their cardiologist. Thus, the patients stand to gain some benefit from participating in the study.
 
Overall, our study team determined that benefits significantly outweigh the risks to the patients participating in this study.

Number of sites enrolling participants	Emory University Hospital/Emory University Midtown Hospital/Emory St. Joseph's Hospital.
Study duration	20 years.
Participant duration	1 year from the time of surgery.

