#### **5.0 TREATMENT OPTIONS**

Patients recruited to this study, are determined by their cardiologists to be suitable for correction of their FMR to improve their health. A transthoracic echo has been performed on them, which

[figure not shown]
depicts moderate or greater severity of FMR, and thus they were referred to us for intervention. The patients may receive mitral valve repair or mitral valve replacement, depending on their choice along with advice from the physician team. Risks and benefits of both the treatment options will be explained to the patient. If mitral valve repair is planned in these patients, they will be recruited to this study. If mitral valve replacement is planned, they will not be recruited to this study. If mitral valve repair is planned, but intra-procedurally the physician decides that mitral valve replacement is more apt, they will continue in the study. If mitral valve replacement is planned, but intra-procedurally the physician decides that mitral valve repair is more apt, they will continue in the study.

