## 11.0 ANALYSIS PLAN

**General design issues:** This is an observational, prospective, non-randomized, single center, multiple phase study. Enrolled patients will have clinically significant FMR with either ischemic or non-ischemic cardiomyopathies. 50 patients are recruited to phase 1 (all 50 receiving undersizing mitral annuloplasty), and 90 patients to phase 2 (75 receiving undersizing mitral annuloplasty and 15 receiving undersizing mitral annuloplasty and papillary muscle approximation). In patients

receiving undersizing mitral annuloplasty, the same rigid annuloplasty ring will be used as consistently as possible, and up to two sizes of downsizing will be performed as consistently as possible. In some patients recruited to the study, the surgeon may decide to switch to mitral valve replacement, or may perform a repair and deem it to be a failure and then switch to mitral valve replacement. In either case, the patient will continue to be part of the study, but with follow-up performed only at 12 months.

**Sample size estimation and statistical analysis plan:** The primary objective of this study is to determine the correlation between pre-operative inter-papillary muscle separation and the 6 month and 12 month post-operative FMR grade after undersizing mitral annuloplasty. Pre-operative inter-papillary muscle separation will be measured and is a continuous variable, while the recurrence of FMR will be deemed binary (1: if MR greater than or equal to 2+ severity observed at 12 months; 0: if MR less than or equal to 2+ severity observed at 12 months). An ROC curve analysis will be used to determine the inflection point of inter-papillary muscle separation at which FMR will recur at 12 months after annuloplasty. Sample sizes are based on previously published data, and on ensuring the ability to detect with high probability, a clinically meaningful presumed benefit for patients undergoing mitral valve repair.

Recruitment to the papillary muscle approximation arm is not based on power analysis as it is only a pilot study.

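### The inclusion lists state concomitant right-sided valve surgery as a criterion without saying whether it is required or permitted, and read literally this contradicts the study population described elsewhere

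*Combined protocol and SAP*

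**What the plan says.** Section 1.0 (Inclusion criteria) has five items: mitral regurgitation of at least moderate grade, cardiomyopathy, a right-sided procedure, adult age, and ability to consent. The third reads "Concomitant right sided valve repair or replacement (i.e. patients requiring concomitant tricuspid procedures". Section 7.2 repeats it in the same words. The item directly above it is "Cardiomyopathy of ischemic or non-ischemic origins, with or without the need for coronary revascularization".

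Elsewhere the study population carries no right-sided condition:

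- Section 1.0, Population: patients "referred for surgical or transcatheter mitral valve annuloplasty with or without the need for revascularization", with suitability left to the surgeon on ventricular diameter and tenting height.
- Section 5.0: "If mitral valve repair is planned in these patients, they will be recruited to this study".
- Section 7.2, Surgical procedures: annuloplasty alone, or annuloplasty plus papillary muscle approximation. Neither description has a tricuspid step.
- Section 11.0: "Enrolled patients will have clinically significant FMR with either ischemic or non-ischemic cardiomyopathies".

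The planned size is "140 subjects in total at Emory University", at about 25 per year. Section 1.0 gives a study duration of 20 years and one year of participation per patient.

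**The concern.** An inclusion list is normally read as a set of conditions that must all be met. On that reading the right-sided item is a requirement, and most of the rest of the protocol describes a different and wider population.

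The item is used in three ways. Registry 1 screens against the inclusion and exclusion criteria (sections 1.0 and 7.2). Registries 2 and 3 select charts of patients who would have qualified, with Registry 3 reaching back to 2004. Section 10.0 (Monitoring) places eligibility among the data verified in full against source. A screener who follows the words turns away patients whom section 5.0 says to recruit. A screener who follows section 5.0 enrols patients who fail a written criterion. Over a long study with several screeners, both could happen.

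What is at stake is the composition of the cohort. The primary objective and the planned cut-off (sections 2.0, 3.0 and 11.0) concern annuloplasty for functional mitral regurgitation in general. If the item were enforced, the cut-off would come only from patients who also had right-sided surgery. If it were applied unevenly, the cohort would be a mixture determined by who did the screening.

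**Working it through.** **Step 1. Are the items cumulative?** Neither list says so. If they were alternatives, being an adult would be enough to qualify, which cannot be meant. Severity, cardiomyopathy, age and consent must therefore hold together, and nothing exempts the right-sided item.

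**Step 2. Is the item marked as optional?** The protocol marks options elsewhere. The revascularization item directly above does so, and the congenital heart disease exclusion names its exceptions. The right-sided item has no such phrase, and its gloss describes patients who need the procedure. The wording is the same in both lists, so it is not a slip in one of them.

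**Step 3. Does the literal reading agree with the rest?** A patient with moderate or greater functional regurgitation, planned mitral repair and no tricuspid procedure is classified as follows:

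| Place | Result for this patient |
|---|---|
| 1.0 and 7.2, Inclusion criteria (literal) | not eligible |
| 1.0, Population | in the population |
| 5.0, recruitment rule | recruited |
| 7.2, Surgical procedures | operation as described |
| 11.0, enrolled patients | as described |

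The two inclusion lists stand against the four other places.

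**Step 4. Can an effect on accrual be shown?** Inputs from section 1.0: "125 patients to receive UMA and followed to 12 months, with interim imaging"; "15 patients to receive UMA with PMA and followed to 12 months, with interim imaging"; about 25 per year; 20 years in all; one year of follow-up.

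- Total: 125 + 15 = 140, which reproduces the plan's figure. By phase (section 11.0): 50 + 75 + 15 = 140. This checks the sum only; section 11.0 gives no alpha, power or effect size.
- Accrual time as planned: 140 / 25 = 5.6 years.
- If 25 per year counts all repair candidates (assumption) and a share f of them needs a tricuspid procedure (assumption; not in the documents), accrual time is 140 / (25 × f):

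| f | per year | years |
|---|---|---|
| 0.75 | 18.75 | 7.5 |
| 0.50 | 12.5 | 11.2 |
| 0.40 | 10 | 14.0 |
| 0.30 | 7.5 | 18.7 |
| 0.20 | 5 | 28.0 |

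- Enrolment time available: 20 − 1 = 19 years. Smallest share that still reaches 140: 140 / (25 × 19) = 0.295.
- If 25 per year already counts only patients who meet the literal criteria, the time stays at 5.6 years.

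Accrual would therefore overrun the stated duration only if the 25 refers to the wider pool and the share is below about 0.295. The documents settle neither point.

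**The case against.** The strongest reply is that the intent can be recovered. No sentence says that every item must be met, the gloss can be read as naming a group who are admitted, and the population, recruitment rule, operations and analysis plan all point to permission. On this view it is loose drafting that experienced staff would read correctly, and no endpoint, sample size or analysis depends on it.

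Much of that stands. This is a drafting ambiguity, not a demonstrated restriction of who is enrolled. But the inclusion list is the text that screeners and monitors apply, and it should not have to be corrected by inference from other sections.

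A reader might infer more than the documents support:

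- *That accrual fails.* The basis of the yearly figure and the tricuspid share are both missing, and the 20-year duration accommodates a wide range of shares.
- *That a given number of enrolled patients would be eligibility deviations.* Any count needs the same missing share, and section 10.0 does not say how an ambiguous criterion is to be interpreted.
- *That an analysis of eligible patients would lose many of them.* Section 11.0 defines no such analysis set, and it keeps even patients switched to valve replacement.
- *That patients with right-sided surgery differ in recurrence or mortality.* The documents report neither by tricuspid status.

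**Conclusion.** The concern holds as an internal contradiction in the eligibility rule. In both inclusion lists the right-sided item, read literally with its neighbours, excludes patients whom the population statement, the recruitment rule, the described operations and the analysis plan include. This rests on the ordinary convention that inclusion items are cumulative, which the other items in the list bear out.

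The consequence is a risk of inconsistent screening, or of a narrower cohort for the cut-off. The documents do not allow that risk to be sized. The total of 140 and the 5.6 years of accrual implied by the plan's own rate are not shown to be wrong, and no power figure is affected. It should be corrected because the item governs who enters the study and the correction is trivial.

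**What to change.** Reconcile the inclusion lists in sections 1.0 and 7.2 with the Population entry in 1.0, the recruitment rule in 5.0, the operations in 7.2 and the enrolled patients in 11.0. State in both lists, in the same words, whether a concomitant right-sided procedure is required or merely permitted. The other sections all read as permitted; if that is what the sponsor means, the optional form already used for revascularization would serve. If a requirement is meant, those four places need to say so.

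Screeners for all three registries should be told which reading applies, and the coordinator should check that patients already screened were handled accordingly.

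The cost is a one-line amendment in two places. If the procedure is permitted, no stated figure changes: the total stays at 140 and the implied accrual time at 5.6 years.
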